3.1 Lenalidomide

3.1.1 Introduction

Lenalidomide is a proprietary IMiD™ compound of Celgene Corporation. IMiD™ compounds have both immunomodulatory and anti-angiogenic properties which could confer anti-tumor and anti-metastatic effects. Lenalidomide has been demonstrated to possess anti-angiogenic activity through inhibition of bFGF, VEGF and TNF-alpha induced endothelial cell migration, due at least in part to inhibition of Akt phosphorylation response to bFGF (16). In addition, lenalidomide has a variety of immunomodulatory effects. Lenalidomide stimulates T cell proliferation, and the production of IL-2, IL-10 and IFN-gamma, inhibits IL-1 beta and IL-6 and modulates IL-12 production(17). Upregulation of T cell derived IL-2 production is achieved at least in part through increased AP-1 activity(18).

Although the exact anti-tumor mechanism of action of lenalidomide is unknown, a number of mechanisms are postulated to be responsible for lenalidomide's activity against multiple myeloma. Lenalidomide has been shown to increase T cell proliferation, which leads to an increase in IL-2 and IFN-gamma secretion. The increased level of these circulating cytokines augment natural killer cell number and function, and enhance natural killer cell activity to yield an increase in multiple myeloma cell lysis(19). In addition, lenalidomide has direct activity against multiple myeloma and induces apoptosis or G1growth arrest in multiple myeloma cell lines and in multiple myeloma cells of patients resistant to melphalan, doxorubicin and dexamethasone(20).

3.1.2 INDICATIONS AND USAGE:

Revlimid® (lenalidomide) is indicated for the treatment of patients with transfusion-dependent anemia due to Low- or Intermediate-1-risk myelodysplastic syndromes associated with a deletion 5q cytogenetic abnormality with or without additional cytogenetic abnormalities. Revlimid® is also approved in combination with dexamethasone for the treatment of patients with multiple myeloma that have received at least one prior therapy.

3.1.3 Adverse Events

Most frequently reported adverse events reported during clinical studies with lenalidomide in oncologic and non-oncologic indications, regardless of presumed relationship to study medication include: anemia, neutropenia, thrombocytopenia and pancytopenia, abdominal pain, nausea, vomiting and diarrhea, dehydration, rash, itching, infections, sepsis, pneumonia, UTI, upper respiratory infection, cellulitis, atrial fibrillation, congestive heart failure, myocardial infarction, chest pain, weakness, hypotension, hypercalcemia, hyperglycemia, back pain, bone pain, generalized pain, dizziness, mental status changes, syncope, renal failure, dyspnea, pleural effusion, pulmonary embolism, deep vein thrombosis, CVA, convulsions, dizziness, spinal cord compression, syncope, disease progression, death not specified and fractures.

Complete and updated adverse events are available in the Investigational Drug Brochure and the IND Safety Letters.

3.2 Azacitidine (Vidaza®)

3.2.1 Introduction

Azacitidine is an azanucleoside analogon, which was developed in the early 1960s as a cytotoxic agent(21). A number of studies have looked at different parenteral doses and schedules of azacitidine, finding maximum tolerated doses of up to 500 mg/m² when administered weekly(22). Almost 20 years after the original development, azacitidine was found to inhibit the methylation of newly synthesized DNA by inhibiting DNA methyltransferase (DNMT)(7-9), leading to differentiation of human cell lines(23) and reversing oncogenic silencing of tumor suppressor genes(24). Early trials used high doses of the drug that predominantly had nucleoside analogue-type cytotoxic effects but in recent years lower doses, that can induce DNA demethylation in vivo (25)have been used successfully in MDS and AML, improving survival compared to conventional care regimens in high risk MDS and WHO AML patients in a recent phase III trial(10).

3.2.2 INDICATIONS AND USAGE

Azacitidine is indicated for treatment of patients with the following French-American-British (FAB) myelodysplastic syndrome subtypes: refractory anemia (RA) or refractory anemia with ringed sideroblasts (if accompanied by neutropenia or thrombocytopenia or requiring transfusions), refractory anemia with excess blasts (RAEB), refractory anemia with excess blasts in transformation (RAEB-T), and chronic myelomonocytic leukemia (CMMoL).

3.2.3 Adverse Events

The most frequently reported adverse events reported during clinical studies with azacitidine, regardless of presumed relationship to study medication include: Gastrointestinal events (nausea, vomiting, diarrhea, constipation, and anorexia), neutropenia, febrile neutropenia, thrombocytopenia, injection site events, arthralgia, dizziness, dyspnea, cough, and myalgia.

Complete and updated adverse events are available in the Investigational Drug Brochure and the IND Safety Letters.

3.3 Rationale for Use in Relapsed or Refractory Multiple Myeloma

With an incidence of 5.6/100,000 multiple myeloma is the second most common hematologic malignancy after Non-Hodgkin lymphomas (SEER 2001-2005). It remains an incurable disease and in the setting of second line or later treatment the progression-free survival ranged between 6-12 months with an overall survival between 1.5 and 3 years in recent trials(1). One of the most successful regimens combined lenalidomide at 25mg on 21 days of a 28 day cycle with dexamethasone in pulse fashion at 40mg day 1-4, 9-12, 17-20 of the first 4 cycles followed by administration from day 1-4 only in US

patients (11). The majority of patients in this trial had been treated with at least 2 prior regimens. The median time to progression was 11.1 months in patients treated with the combination compared to 4.7 month with dexamethasone alone. Although the majority of dexamethasone-only treated patients received lenalidomide at relapse, the median overall survival was superior in the group randomly assigned to combination therapy (29.6 months versus 20.2 months). In Europe and Australia this regimen yielded similar results(26) leading to approval of lenalidomide in combination with dexamethasone for patients with myeloma who have been treated with at least one prior regimen in the US and Europe and for relapsed or refractory myeloma in Australia. A more recent trial randomly assigned newly diagnosed myeloma patients to a lower dexamethasone dose (40mg weekly) or to pulsed dexamethasone in combination with lenalidomide (Rd vs. RD, respectively) and found an improved 2 year overall survival ($p=0.006$) of 87% (Rd) vs. 75% (RD) at the most recently published analysis(12), suggesting at least equivalent outcome with a trend for lower toxicity, especially regarding venous thromboembolism(27). This finding was rapidly translated into clinical practice in the front-line and relapsed setting and is the regimen used in ongoing clinical trials (FIRST trial, SO777).

To further improve the outcome of patients with relapsed and/or refractory multiple myeloma, resistance mechanisms towards available therapies and immune surveillance need to be overcome. In the course of myeloma progression genetic and epigenetic changes accumulate(2-4, 6, 28-34). The latter are most stable if mediated by DNA methylation of promoter regions which confers heritable silencing of tumor suppressor genes favoring apoptosis resistance, cell cycle dysregulation, and immune escape(2-6, 28-32, 35-41). Azacitidine can reverse such silencing and has been shown to have anti-myeloma activity in vitro and in mouse xenografts as a single agent and in combination therapy by overcoming apoptosis resistance as exemplified in a myeloma cell line with a silenced pro-apoptotic gene, called XAF-1(35, 42). The genome wide activity of DNA methyltransferase I (DNMT1) inhibitors like azacitidine offers a mechanism to overcome apoptosis resistance mediated by silencing of diverse tumor suppressor genes in different myeloma clones of individual patients and patient populations as illustrated by in vitro studies of resistance to interferon-induced apoptosis in kidney cancer cell lines(37). Reactivation of tumor antigens and immunomodulatory genes by DNMT1 inhibition (37) may further increase the activity of immunomodulatory drugs and intrinsic immune responses as suggested by an encouraging 31% response rate of melanoma patients treated with decitabine, the in vivo DNA demethylating metabolite of azacitidine, and interleukin-2 in a phase I trial(43). After prolonged exposure to low doses of aza nucleosides in vitro, cancer cells may undergo cell death via differentiation, senescence, or direct apoptosis, likely depending on the methylation profile. Interestingly, healthy human hematopoietic stem cells can be expanded in vitro by decitabine(44, 45). Indirect evidence for expansion of the healthy stem cell pool in vivo comes from the observation that overall survival can be extended independent of a complete response in MDS(10), a disease that can be fatal due to a lack of normal hematopoietic stem cells. Such an expansion of healthy stem cells would have added benefit in myeloma patients who undergo hematopoietic stem cell harvesting for high dose chemotherapy and autologous stem cell rescue.

In MDS azacytidine at 75mg/m² d1-5 every 28 days or 50mg/m² d1-5 and 8-12 every 28 days was relatively well tolerated in combination with lenalidomide 5-10mg daily and showed promising activity with an overall response rate of 71% and a complete response rate of 41%, suggesting the two drugs can be combined synergistically without excess toxicity(46). The FDA approved regimen of azacitidine, 75mg/m² day 1-7 every 28 days for the treatment of MDS leads to maximal blood concentrations that, while lower than in the original studies, are still directly cytotoxic in vitro(47) which could limit the tumor suppressor gene reactivating function by inhibiting DNA duplication which is required for DNA demethylation. It furthermore likely contributes to side effects that make a treatment interruption of three weeks necessary to allow for recovery when the standard MDS schedule is used (75mg/m² d1-7 every 28 days). Unfortunately this also leads to DNA re-methylation before a new cycle begins (25, 48, 49). Furthermore, in diseases with a lower proliferative rate, like multiple myeloma, only a minority of cells would be expected to reactivate tumor suppressor genes if the drug was only given on one out of four weeks. In vitro, non-toxic single low doses of azacitidine (1µM) can reactivate tumor suppressor genes in myeloma cell lines for 3-7 days (unpublished observations). Doses higher than 2-5µM, depending on the cell type, can exert immediate toxicity likely related to nucleoside analogue properties of the drug. Pharmacokinetic data in humans suggest that a single dose of 50mg/m² subcutaneously reaches concentrations that should be sufficient for DNA demethylation but could cause classical nucleoside analogue toxicity in some patients (2.89µM +/- 1.35 µM SD), higher doses like 75mg/m² reach 4.88 µM +/- 1.4µM SD and thus almost certainly exert classic nucleoside analogue toxic effects (13). In this study we aim to avoid pronounced nucleoside analogue side effects while maximally exploiting DNA demethylating effects of azacitidine. We will therefore assess the safety of combination therapy with azacitidine given at low but increasing doses up to 50mg/m² twice a week, together with standard dose lenalidomide and low dose dexamethasone in relapsed or refractory myeloma patients in a phase I/II study with 10 additional patients enrolled at the highest tolerated low azacitidine dose to obtain an initial impression of efficacy and to evaluate whether this dose exerts the expected pharmacodynamic effects in myeloma cells before a larger phase II trial may be conducted.

4 Study Objectives and Endpoints

4.1 Objectives

4.1.1 Primary Objective

- Define the highest tolerated low doses (HTLD and HTLD-CKD for GFR > 60 ml/min and 30-59ml/min, respectively) and safety of azacitidine given at low but increasing doses up to 50mg/m² twice a week concurrently with GFR-adjusted lenalidomide doses and low dose dexamethasone in patients with relapsed or refractory multiple myeloma.

4.1.2 Secondary Study Objectives

- Response according to international response criteria (\geq PR) and clinical benefit response (\geq minor response according to adapted EBMT criteria), see under 7
- Correlate response with plasma activity of the azacitidine inactivating enzyme cytidine deaminase (CDA)
- Progression-free survival and overall survival
- Peripheral blood hematopoietic progenitor (CD34+) yield and time to neutrophil and platelet recovery in patients undergoing autologous stem cell transplantation
- Promoter demethylation and gene reactivation in myeloma cells and hematopoietic progenitors treated at the HTLD / HTLD-CKD level after cycle 1
- Changes in global gene expression in myeloma cells treated at the HTLD / HTLD-CKD level after cycle 1

4.2 Endpoints

4.2.1 Primary Endpoint

- The highest tolerated low dose (HTLD and HTLD-CKD for GFR > 60 ml/min and 30-59ml/min, respectively) of azacitidine in combination with GFR-adjusted lenalidomide will be defined as the highest dose level studied (up to 50mg/m² twice a week) at which dose limiting toxicity (DLT) occurs during the first 28-day cycle in ≤ 1 out of 6 patients. If one out of the first 3 patients with GFR ≥ 60 ml/min develops DLT, up to three additional patients are treated at the same dose level. In patients with GFR 30-59ml/min each dose level will enroll 6 patients unless more than 1 patient develops DLT.. Any dose level evaluated as the possible HTLD / HTLD-CKD must include 6 patients assessed for DLT. DLT is defined in Section 5.1. Toxicity according to CTCAE v.4.0 will be assessed with weekly CBC w. Diff and CMP during the first 6 cycles, then before each cycle, weekly history and physical during the first 28-day cycle, then before each cycle until cycle 12.

4.2.2 Secondary Endpoints

- Response will be determined monthly during the first 12 cycles and every two months thereafter with serum and 24hr urine protein electrophoresis, and as appropriate, supplemented by immunofixation, serum free light chain assay, and bone marrow examination. Response before high dose melphalan and autologous stem cell transplant will also be confirmed by two separate blood and 24 hr urine tests between the last dose of combination therapy and the first dose of the mobilizing agent.

- Plasma from peripheral blood draws will be used to quantify the activity of CDA using an HPLC method (see under 5.5.3)
- Progression-free survival will be measured from study entry to progression as defined by international response criteria (see under 5.9.1) or death of any cause, whichever comes first.
- Overall survival will be measured from study entry to death from any cause.
- CD34+ cell yield will be calculated based on flow cytometry of mononuclear cells harvested following stem cell mobilization. Time to neutrophil ($\geq 1,000/\text{mm}^3$) and platelet ($\geq 100,000/\text{mm}^3$) recovery will be counted from the day of stem cell infusion (=day 0)
- Promoter demethylation and gene reactivation will be measured at least at the HTLD / HTLD-CKD level using the Illumina® HumanMethylation27 BeadChip array on CD138 purified and CD34 purified cells obtained from bone marrow aspirates within 7 days before treatment start and at the end of cycle #1. RNA will be harvested from the same cell populations to confirm reactivation of selected genes identified on the array. Since the HTLD / HTLD-CKD is identified retrospectively DNA and RNA will be isolated from purified cell populations from all bone marrow aspirations before and after cycle #1.
- The RNA harvested from myeloma cells before and after the first cycle of therapy at the HTLD / HTLD-CKD level will furthermore be used to identify changes in global gene expression using the Illumina® HT12 array.

5 Investigational Plan

5.1 Overall Design

This phase I/II trial will use a classical 3x3 design to determine the highest tolerated low dose (HTLD) for patients with GFR $\geq 60 \text{ ml/min}$ (Cockroft-Gault) and a modified 3x3 design to identify the highest tolerated low dose for patients with GFR 30-59 ml/min (HTLD-CKD) with additional enrollment of 10 patients at the highest tolerated low doses (HTLD / HTLD-CKD) of azacitidine.

Dose levels are outlined under 5.6.2.3.

Dose limiting toxicity (DLT) is defined as one of the following drug-related toxicities occurring during the first 28-day cycle (if a DLT is attributed to progressive disease, it will not be counted as a DLT):

- Any CTCAE v.4.0 grade ≥ 3 non hematologic toxicity (including febrile neutropenia)
 - For nausea, vomiting, or diarrhea, subjects must have a Grade 3 or 4 event that persists at this level despite the use of optimal symptomatic treatment, in order for these events to be considered a DLT

- Grade 4 transaminitis (serum transaminase $> 20 \times$ upper limit of normal [ULN]) is a DLT, while Grade 3 transaminitis (serum transaminase $> 5 \times$ and $\leq 20 \times$ ULN) must be present for ≥ 7 days to be considered a DLT
- Grade 3 or 4 venous thromboembolic events are not considered to be DLTs as long as anticoagulant therapy can be administered (see Section 6.5.3 and 6.6.2)
- Grade 3 or 4 hypokalemia, hypophosphatemia, hypomagnesemia or hyponatremia that responds to electrolyte supplementation within 7 days would not qualify as a DLT.
- CTCAE v.4.0 grade ≥ 4 neutropenia or thrombocytopenia that does not resolve to grade ≤ 3 within seven days of holding azacitidine and lenalidomide. While platelet transfusions are allowed at the discretion of the treating physician to maintain 100% dose level, any grade ≥ 4 thrombocytopenia that is followed by platelet transfusion prior to resolution to grade ≤ 3 will be counted as DLT.

Dose escalation for patients with GFR $\geq 60\text{ml/min}$:

At least 3 patients will be treated in each dose level tested beginning with dose level 1. At any dose level, if none of the first 3 evaluable patients experience DLT in the first 28 day cycle, the next three patients will be treated at the next dose level. At any dose level, if DLT occurs in one out of three patients during the first 28 day cycle, up to 3 additional patients will be treated at the same dose level. If no DLT occurs in the additional 3 patients, subsequent 3 patients will be treated at the next dose level. Once DLT occurs in 2 patients treated at a given dose level no further patients will be accrued at this dose level but patients already on treatment will continue according to study protocol. If DLT occurs in 2 patients treated at a given dose level, the next lower dose level will be evaluated as the possible HTLD, and if only 3 patients had been enrolled at this dose level, an additional 3 patients will be enrolled to properly assess this dose level as the possible HTLD. The dose level at which DLT occurs in ≤ 1 out of 6 patients will be defined as the highest tolerated low dose (HTLD) and ten more patients will be accrued at this dose level. Six evaluable patients must be assessed for DLT at any dose level that is being considered as the HTLD. Patients experiencing a DLT during their first 28-day cycle may remain on study with appropriate dose reduction (5.7.3).

Dose escalation for patients with GFR 30-59ml/min:

Only two dose levels of azacitidine will be tested in combination with fixed dose lenalidomide. Starting with dose level “CKD 1” (DL CKD1), 3 patients will initially be enrolled and if no more than 1 experience DLT, 3 additional patients will be enrolled at the same dose level. If no more than 1 out of 6 patients treated at DL CKD1 develop DLT, subsequent patients will be enrolled at DL CKD2. Once 2 of 3 or 2 of up to 6 patients treated at a given dose level develop DLT, no further patients will be enrolled at that dose level. If this occurs at DL CKD1, subsequent patients will be enrolled at DL CKD-1. If it occurs at DL CKD2, DL CKD1 will be defined as HTLD-CKD. If 2 of 3 or 2 of up to 6 patients treated at DL CKD-1 develop DLT, the tested azacitidine / lenalidomide / dexamethasone regimen will be considered intolerable for patients with

GFR 30-59 ml/min. The highest dose level that causes DLT in no more than 1 out of 6 evaluable patients will be considered the HTLD-CKD and once this is defined additional patients treated at this dose level may contribute to the 10 patient phase II extension. Patients experiencing a DLT during their first 28-day cycle may remain on study with appropriate dose reduction (5.7.3).

[figure not shown]
Patients that are not evaluable for DLT throughout the first 28 day cycle of the dose escalation portion of the study due to progressive disease or for other reasons, will be replaced.

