5.7 Dose Continuation, Modification and *Interruption*

Subjects will be evaluated for AEs at each visit with the NCI CTCAE v.4.0 (Appendix III: NCI CTCAE v.4.0) used as a guide for the grading of severity. Sections below describe recommended dose reduction steps, instructions for initiation of a new cycle of therapy and dose modifications during a cycle of therapy. Clinical judgment may be used when deciding which drug to hold or modify in scenarios that are not covered below. Patients encountering a dose-limiting toxicity during their first cycle may remain on study with appropriate reduction steps.

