5.7.3 Dose Re-Escalation Guidelines

Dose Re-Escalation Upon Recovery from Hematologic Adverse Events

If the dose of lenalidomide or azacitidine was reduced due to dose limiting hematologic toxicity and continued treatment results in improvement of bone marrow function, dose increases by one dose level and drug at a time may be performed if the ANC is ≥ 1000 /mm³ and platelets are $\geq 50,000$ /mm³ at day one of the respective cycle if the previous cycle was completed without dose modifications due to toxicity (regardless of type). If patient's myeloma has previously been refractory to lenalidomide consideration should be given to increase azacitidine first, otherwise lenalidomide should be increased first. In general, drug dosing increases should alternate between lenalidomide and azacitidine until target doses of both drugs are reached or toxicity occurs but the treating physician may use clinical judgment and first increase one drug to target dose. After 12 months since initiation of protocol therapy, no further lenalidomide dose titration is permitted.

Dose Re-Escalation Upon Recovery of Kidney Function

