5.7.5 Instructions for Dose Modifications or Interruption During a Cycle

Table 5 outlines instructions for dose reductions of study drugs for specific toxicities. Study drugs may be temporarily or permanently dose reduced using doses outlined in table 1-4 or temporarily discontinued in other situations where their continued administration according to protocol is felt unsafe by the treating physician.

Table 5: Dose Modifications Azacitidine and Lenalidomide

NCI CTC Toxicity Grade	Dose Modification Instructions
Grade 3 neutropenia associated with fever (temperature $\geq 38.5^{\circ}$ C) or Grade 4 neutropenia	
 • Hold (interrupt) lenalidomide and, while on combination, also azacitidine dose. • Follow CBC weekly. • During combination therapy with lenalidomide and azacitidine: 
 ◦ If neutropenia has resolved to \leq grade 2 prior to Day 21 of the current cycle, restart azacitidine at the next lower dose level and continue lenalidomide at the same dose level if the patient's myeloma has not previously been refractory to lenalidomide, otherwise maintain azacitidine dose level and reduce lenalidomide by one dose level (if the patient is only on one of these drugs reduce its dose by one level) and continue treatment through the scheduled end of the cycle. Otherwise, omit treatment for the remainder of the cycle and reduce dose levels in the same way at the start of the next cycle. Omitted doses are not made up. ◦ If neutropenia is the only toxicity for which a dose reduction is required (no fever or other reason to reduce doses), G-CSF should be considered instead of a dose reduction. • During maintenance therapy with lenalidomide: 
 ◦ If neutropenia has resolved to \leq grade 2 prior to Day 21 of the current cycle, restart lenalidomide at the next lower dose level, and continue through the scheduled end of the cycle. Otherwise, omit lenalidomide for the remainder of the cycle and reduce lenalidomide by 1 dose level at the start of the next cycle. Omitted doses are not made up.

Table 5: Dose Modifications Azacitidine and Lenalidomide

NCI CTC Toxicity Grade	Dose Modification Instructions

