Thrombocytopenia \geqGrade 3 (platelet count $< 50,000/\text{mm}^3$)	
 During the first 4 cycles platelet transfusions may be used at the discretion of the treating physician to achieve platelet counts $\geq 50,000/\text{mm}^3$ on post-transfusion CBCs and thereby maintain the current dose level of lenalidomide and azacitidine. If platelet transfusions are administered, the CBC should be monitored at least twice a week. For thrombocytopenia \geq grade 3 ($< 50,000/\text{mm}^3$) after platelet transfusion or if platelet transfusions are not used hold (interrupt) lenalidomide and, while on combination, also azacitidine dose. If thrombocytopenia \geq grade 4 ($< 25,000/\text{mm}^3$) on a pre-platelet transfusion CBC or if platelet transfusions are not used hold prophylactic anticoagulation Follow CBC weekly, if given platelet transfusions twice a week. If thrombocytopenia resolves to \leq grade 4 ($\geq 25,000/\text{mm}^3$) and last platelet transfusion ≥ 7 days ago resume prophylactic anticoagulation. During combination therapy with lenalidomide and azacitidine: 
 If thrombocytopenia resolves to \leq grade 2 (with or without the use of platelet transfusions) prior to Day 21 of the current cycle, restart azacitidine at the next lower dose level and lenalidomide at the same dose level if the patient's myeloma has not previously been refractory to lenalidomide, otherwise maintain azacitidine dose level and reduce lenalidomide by one dose level (if the patient is only on one of these drugs reduce its dose by one level). Otherwise, omit treatment for remainder of cycle and reduce dose levels in the same way at the start of the next cycle. Omitted doses are not made up. During maintenance therapy with lenalidomide: 
 If thrombocytopenia has resolved to \leq grade 2 prior to Day 21 of the current cycle, restart lenalidomide at the next lower dose level, and continue through the scheduled end of the cycle. Otherwise, omit lenalidomide for the remainder of the cycle and reduce lenalidomide by 1 dose level at the start of the next cycle. Omitted doses are not made up.

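### Section 5.1 ties staying on study after a cycle-1 DLT to dose reduction, but it cites 5.7.3, which covers only re-escalation, and Table 5 lets some DLT patients continue both drugs at the current dose

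*Combined protocol and SAP*

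**What the plan says.** Section 5.1 gives the same sentence at the end of the escalation rules for each renal cohort: "Patients experiencing a DLT during their first 28-day cycle may remain on study with appropriate dose reduction (5.7.3". The introduction to 5.7 repeats the condition without the pointer: "Patients encountering a dose-limiting toxicity during their first cycle may remain on study with appropriate reduction steps".

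The cited section is headed "5.7.3 Dose Re-Escalation Guidelines". Its two parts cover recovery of blood counts ("Dose Re-Escalation Upon Recovery from Hematologic Adverse Events") and recovery of kidney function. The instructions for lowering doses are in 5.7.5, where "Table 5 outlines instructions for dose reductions of study drugs for specific toxicities".

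In the neutropenia row, Table 5 holds both drugs. For a patient whose myeloma was not refractory to lenalidomide, it then says to "restart azacitidine at the next lower dose level and continue lenalidomide at the same dose level"; for a refractory patient, lenalidomide goes down and azacitidine stays. The same row adds that, where neutropenia is the only toxicity calling for a reduction, "G-CSF should be considered instead of a dose reduction".

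In the thrombocytopenia row, transfusion may be used during the first 4 cycles, at the treating physician's discretion, to reach at least 50,000/mm³ "on post-transfusion CBCs and thereby maintain the current dose level of lenalidomide and azacitidine". If the post-transfusion count is below 50,000/mm³, or transfusion is not used, both drugs are held and one is restarted a level lower.

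**The concern.** A patient whose event counts against a dose level should have one unambiguous instruction for what dose comes next. Section 5.1 and the 5.7 introduction make reduction the condition for staying on study. Table 5 offers two ways to continue without reduction and does not mention cycle-1 DLTs. The section that 5.1 cites does not settle the matter.

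Two things are at stake. The first is the safety of the patient, who may go on receiving the dose that produced the DLT. The second is the reading of later cycles: section 10.2.2 reports adverse events by dose level treated, and patients reduced and not reduced after a DLT would sit in the same group without a rule that says which to expect. The trial runs at two institutions, so the same event could be handled differently depending on which section is followed.

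**Working it through.** The plan gives no figure to reproduce. The check follows each hematologic DLT route in 5.1, and febrile neutropenia, through Table 5 and 5.7.4.

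| DLT route in 5.1 | What Table 5 does | Can both drugs stay at the current dose? |
|---|---|---|
| Grade 4 thrombocytopenia transfused before it resolves | Transfusion may maintain both drugs if the post-transfusion count is ≥ 50,000/mm³; a pre-transfusion count < 25,000/mm³ stops only prophylactic anticoagulation | Yes, by the transfusion option |
| Grade 4 thrombocytopenia unresolved after seven days off both drugs | Drugs already held; restart with one drug a level lower | No, the default reduction applies |
| Grade 4 neutropenia unresolved after seven days off both drugs, no fever | Default: one drug a level lower; G-CSF to be considered in its place | Yes, if the G-CSF option is taken to apply |
| Febrile neutropenia (listed as non-hematologic) | One drug a level lower; the G-CSF option requires absence of fever | No |

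**Transfusion route.** The sentence in 5.1 that scores the transfused event as a DLT also allows transfusion to keep full dose. Section 5.7.4 does not close the gap. Its one-level reduction applies when dosing was omitted for the rest of the cycle or the next cycle was delayed by newly encountered toxicity, and a patient transfused through the event need have neither. Section 5.7.4 also allows transfusion in the first 4 cycles to reach the platelet threshold for a new cycle. The transfusion clause appears only in 5.1; the DLT definitions in 6.2.1 and 10.2.1 omit it. Under those two definitions the same event would not be a DLT by this route.

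**Neutropenia route.** The conflict is softer. The G-CSF option requires that there be no other reason to reduce, and the DLT sentence in 5.1 could be read as such a reason. If instead the option applies, it can collide with the one-level reduction in 5.7.4 when dosing was omitted for the rest of the cycle.

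**Pointers.** Section 5.7.3 is cited for reductions in 5.1 (twice, once per cohort) and again at the end of 5.7.4. None of these leads to a reduction rule.

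**Exposure left, transfusion route only.** Take a DLT seen on the day-8 count, before that day's doses, at a twice-weekly level:
- Azacitidine: 4 weeks × 2 = 8 doses; 8 − 2 = 6 remain in cycle 1.
- Lenalidomide: 21 − 7 = 14 doses remain in cycle 1.
- Combination cycles: 6 − 1 = 5 remain.

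These counts do not fit the neutropenia route. That event becomes a DLT only after seven days of holding (8 + 7 = day 15), omitted doses are not made up, and a restart within the cycle needs recovery to grade 2 or better before day 21.

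**Number of patients.** An accepted level has at most 1 DLT in 6; a rejected level has at least 2. For the 10 extension patients the documents give no expected DLT rate. At an assumed 10% to 20%, 10 × 0.10 = 1 to 10 × 0.20 = 2 would have a DLT. That counts all DLT types, so the hematologic routes at issue would be some part of it.

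**The case against.** A reader might infer that Table 5 simply keeps full dose after hematologic DLTs. It does not. Its default in both rows is to hold both drugs and then lower one by one level. Full dose is reached only through a discretionary transfusion option, with a platelet threshold, and a G-CSF option that is only to be considered. Thrombocytopenia that fails to resolve after a hold follows the default reduction.

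The pointer to 5.7.3 may be a stale section number. The heading of 5.7.1 already mentions re-escalation, and Table 3 cites 5.7.1.2 for an escalation rule that now stands in 5.7.2. On that inference 5.1 meant to delegate to what is now 5.7.5. This may well be so, but correcting the number does not cure the problem, because 5.7.5 contains the two options that conflict with the condition in 5.1.

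It can also be said that scoring an event and managing the patient were deliberately separated, since 5.1 permits transfusion to keep full dose in the same sentence that scores the DLT. That explains the transfusion clause. It leaves the later sentence in 5.1, and its twin in 5.7, still naming reduction as the condition for remaining on study.

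Later-cycle data are mixed in any case: Table 5 reduces doses in patients without a DLT, and 5.7.2 allows escalation to 75 and 100 mg/m². The principal investigator must also hear of each DLT within one working day (6.2.1), which limits divergence between sites. Both points stand and reduce the consequence for the analysis. They do not tell the treating physician which dose follows a DLT.

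**Conclusion.** The inconsistency is real and narrow. It is plainest for transfused grade 4 thrombocytopenia, where 5.1 scores a DLT and Table 5 permits both drugs to continue unchanged. It is arguable for isolated afebrile neutropenia and depends on how the G-CSF condition is read. The wrong pointer is a matter of fact in three places.

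A reader might go further and infer that dose finding is compromised. The documents do not support that: the event is scored in cycle 1 whatever dose follows, so under the 5.1 definition the DLT count and the HTLD or HTLD-CKD decision are unaffected. Nor does the default path contradict 5.1 because a lenalidomide-refractory patient keeps the full azacitidine dose. One drug is still reduced, and 5.1 does not say which.

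The effect is on care after a DLT and on the interpretation of later-cycle safety, in a handful of patients. The estimate of 1 to 2 in the extension rests on an assumed 10% to 20% rate. Because it bears on patient safety and costs little to correct, it should be fixed.

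**What to change.** Reconcile section 5.1 (both cohorts), the introduction to 5.7, section 5.7.4 and the neutropenia and thrombocytopenia rows of Table 5, so that one stated rule governs dosing after an event scored as a cycle-1 DLT. Say expressly whether the transfusion and G-CSF options are open to such a patient, and which section governs if two appear to apply. Correct the pointers to 5.7.3 in 5.1 (both cohorts) and 5.7.4 so that they name the section holding that rule. Since the transfusion route depends on it, settle at the same time whether the transfusion clause belongs in the DLT definitions of 6.2.1 and 10.2.1. Which clinical rule is right is for the investigators.

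The cost is protocol wording: a sentence or two, matching edits in the two table rows and three cross-references, with the usual amendment review under 8.1. Sample size, visits and data collection do not change.
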